#### 14.1.2 Responsibility for Data Submission

Study participants are responsible for submitting CDUS data and/or data forms to the Coordinating Center quarterly at least 2 weeks before CTEP's due date to allow time for Coordinating Center compilation, Principal Investigator review, and timely submission to CTEP (see Section 14.1.1). The Coordinating Center is responsible for compiling and submitting CDUS data to CTEP for all participants and for providing the data to the Principal Investigator for review.

### 14.2 CTEP Multicenter Guidelines

This protocol will adhere to the policies and requirements of the CTEP Multicenter Guidelines. The specific responsibilities of the Principal Investigator and the Coordinating Center (Study Coordinator) and the procedures for auditing are presented in Appendix I.

The Principal Investigator/Coordinating Center is responsible for distributing all IND Action Letters or Safety Reports received from CTEP to all participating institutions for submission to their individual IRBs for action as required.

Except in very unusual circumstances, each participating institution will order DCTD-supplied agents directly from CTEP. Agents may be ordered by a participating site only after the initial IRB approval for the site has been forwarded by the Coordinating Center to the CTEP PIO ([[contact]](mailto:[contact])) except for Group studies.

### **14.3 Collaborative Agreements Language**

The agent(s) supplied by CTEP, DCTD, NCI used in this protocol is/are provided to the NCI under a Collaborative Agreement (CRADA, Agent-CRADA, CTA, CSA) between the Pharmaceutical Company(ies) (hereinafter referred to as a “Collaborator(s)”) and the NCI Division of Cancer Treatment and Diagnosis. Therefore, the following obligations/guidelines, in addition to the provisions in the “Intellectual Property Option to Collaborator”

(<http://ctep.cancer.gov/industryCollaborations2/default.htm>) contained within the terms of award, apply to the use of the Agent(s) in this study:

1. Agent(s) may not be used for any purpose outside the scope of this protocol, nor can Agent(s) be transferred or licensed to any party not participating in the clinical study. Collaborator(s) data for Agent(s) are confidential and proprietary to Collaborator(s) and shall be maintained as such by the investigators. The protocol documents for studies utilizing investigational Agents contain confidential information and should not be shared or distributed without the permission of the NCI. If a copy of this protocol is requested by a patient or patient’s family member participating on the study, the individual should sign a confidentiality agreement. A suitable model agreement can be downloaded from: <http://ctep.cancer.gov>.
2. For a clinical protocol where there is an investigational Agent used in combination with (an)other investigational Agent(s), each the subject of different collaborative agreements, the access to and use of data by each Collaborator shall be as follows (data pertaining to such combination use shall hereinafter be referred to as “Multi-Party Data”):
  - a. NCI will provide all Collaborators with prior written notice regarding the existence and nature of any agreements governing their collaboration with NIH, the design of the proposed combination protocol, and the existence of any obligations that would tend to restrict NCI's participation in the proposed combination protocol.
  - b. Each Collaborator shall agree to permit use of the Multi-Party Data from the clinical trial by any other Collaborator solely to the extent necessary to allow said other Collaborator to develop, obtain regulatory approval or commercialize its own investigational Agent.
  - c. Any Collaborator having the right to use the Multi-Party Data from these trials must agree in writing prior to the commencement of the trials that it will use the Multi-Party Data solely for development, regulatory approval, and commercialization of its own investigational Agent.

3. Clinical Trial Data and Results and Raw Data developed under a Collaborative Agreement will be made available exclusively to Collaborator(s), the NCI, and the FDA, as appropriate and unless additional disclosure is required by law or court order. Additionally, all Clinical Data and Results and Raw Data will be collected, used, and disclosed consistent with all applicable federal statutes and regulations for the protection of human subjects including, if applicable, the Standards for Privacy of Individually Identifiable Health Information set forth in 45 C.F.R. Part 164.
4. When a Collaborator wishes to initiate a data request, the request should first be sent to the NCI, who will then notify the appropriate investigators (Group Chair for Cooperative Group studies, or PI for other studies) of Collaborator's wish to contact them.
5. Any data provided to Collaborator(s) for Phase 3 studies must be in accordance with the guidelines and policies of the responsible Data Monitoring Committee (DMC), if there is a DMC for this clinical trial.
6. Any manuscripts reporting the results of this clinical trial must be provided to CTEP by the Group office for Cooperative Group studies or by the principal investigator for non-Cooperative Group studies for immediate delivery to Collaborator(s) for advisory review and comment prior to submission for publication. Collaborator(s) will have 30 days from the date of receipt for review. Collaborator shall have the right to request that publication be delayed for up to an additional 30 days in order to ensure that Collaborator's confidential and proprietary data, in addition to Collaborator(s)'s intellectual property rights, are protected. Copies of abstracts must be provided to CTEP for forwarding to Collaborator(s) for courtesy review as soon as possible and preferably at least three (3) days prior to submission, but in any case, prior to presentation at the meeting or publication in the proceedings. Press releases and other media presentations must also be forwarded to CTEP prior to release. Copies of any manuscript, abstract and/or press release/ media presentation should be sent to:

[name].,  
Chief, Regulatory Affairs Branch  

## **15 STATISTICAL CONSIDERATIONS**

### **15.1 Study Design/Endpoints**

The primary objectives of this study are to determine the feasibility and efficacy of the use of molecular profile directed therapies in the treatment of advanced thoracic malignancies. The feasibility rate for the trial will be evaluated by determining the percentage of enrolled patients with a successful molecular profile determined. Efficacy will be determined by assessing if patients who have treatment assigned on the basis of their molecular profiling results will exhibit reasonable response rates to the drug selected for their particular profile.

Patients with NSCLC, SCLC, and thymic malignancies will be eligible for enrollment and each will be considered a separate cohort. In addition, on the basis of the molecular profiling results, one of 5 specific treatments could be assigned to each patient. The particular treatment assignments will be made according to a cascading schema as shown. If no profile of one of the 5 types listed is identified as being appropriate for a given patient, patients will be followed and treated in a separate 'other' (NOS) category.

With 3 disease types and 5 possible specific treatments for each, there are 15 possible treatment arms which will be under active consideration. For each of these 15, the study will be conducted as an optimal two-stage phase II trial (Simon R, Controlled Clinical Trials 10:1-10, 1989).

In all but the arm for patients who have NSCLC and an EGFR mutation, the trial will be conducted in order to rule out an unacceptably low 10% clinical response rate (PR+CR;  $p_0=0.10$ ) in favor of a modestly high response rate of 40% ( $p_1=0.40$ ). For those 14 arms, with  $\alpha=0.05$  (probability of accepting a poor treatment=0.05) and  $\beta = 0.10$  (probability of rejecting a good treatment=0.10), the study will initially enroll 9 evaluable patients in each stratum and if 0 or 1 of the 9 have a clinical response, then no further patients will be accrued. If 2 or more of the first 9 have a response, then accrual would continue until a total of 20 patients have enrolled in that stratum. If there are 2-4 responses in 20 patients, this would be an uninterestingly low response rate in that stratum, while if there were 5 or more responses in 20 patients, then this would be sufficiently interesting to warrant further study in later trials. Under the null hypothesis (10% response rate), the probability of early termination is 77% for a given stratum.

In the arm for patients who have NSCLC and an EGFR mutation, the trial will be conducted in order to rule out an unacceptably low 30% clinical response rate (PR+CR;  $p_0=0.30$ ) in favor of a modestly high response rate of 60% ( $p_1=0.60$ ). The target is higher for these patients since a higher response rate is known to be possible for these patients. For that one arm, with  $\alpha=0.05$  (probability of accepting a poor treatment=0.05) and  $\beta = 0.10$  (probability of rejecting a good treatment=0.10), the study will initially enroll 10 evaluable patients in each stratum and if 0 to 3 of the 10 have a clinical response, then no further patients will be accrued. If 4 or more of the first 10 have a response, then accrual would continue until a total of 28 patients have enrolled in that stratum. Under the null hypothesis (30% response rate), the probability of early termination is 65% for patients in this stratum.

As feasibility is an important endpoint as well, the trial will include an early stopping rule for accrual to specific arms which are not enrolling adequate numbers of patients. After 18 months from the date the first patient enrolls on the trial in any arm, if there are arms with no more than a

single patient, then further accrual to that arm will end. This will prevent continued accrual to arms which are very unlikely to be able to treat sufficient patients for evaluating the first stage (e.g., 9 or 10 patients) within 5 years.

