## **1 OBJECTIVES**

### **1.1 Primary Protocol Objectives**

- 1.1.1 To determine the feasibility of the use of tumor's molecular profiling and targeted therapies in the treatment of advanced stage non-small cell lung cancer (NSCLC), small cell lung cancer (SCLC) and thymic malignancies.
- 1.1.2 To estimate the response rate of molecular-profile directed treatments in NSCLC, SCLC and thymic malignancies patients.

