## 5.3 Enrollment in treatment arms

**Treatment arms are no longer recruiting as of 3/22/16.**

Due to the rapidly progressing course of the thoracic malignancies in this study, treatment decisions will be made in approximately 2 weeks from the time that the tumor samples were obtained. Based on the molecular profiling results, the patients will be offered enrollment into a specific treatment arm according to the decision tree shown in [Figure 2](#) and the eligibility criteria described in [Section 3](#).

Individuals who meet the eligibility criteria for *EGFR* germline mutation testing ([Section 3.4](#)) but who do not have advanced cancer as defined in [Section 3.1.1](#) are not eligible for the treatment arms.

Figure 2. Schema

\* See Sections 3.2 and 3.3 for eligibility criteria for the treatment arms. Patients will be allowed to crossover to different treatment arms as long as they meet eligibility criteria.

† See separate eligibility criteria (Section 3.4) and schema for EGFR germline mutation testing.

No = No or not available

Amp = gene amplification by FISH

NOS = non-otherwise specified arm

**A** = optional re-biopsy for patients that responded to previous line of therapy

Each study arm is independent from the other arms; it has its own eligibility criteria (Section 3) and statistical considerations (Section 15), and will be analyzed independently. Additionally, it is not our intention to compare the outcomes among treatment arms since the patients enrolled in each arm will have different molecular characteristics.

Patients enrolled in one of the treatment arms of this protocol, with the exception of the NOS arm and individuals enrolled for EGFR germline mutation testing only, will be treated and

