#### **5.5 The NOS arm**

All patients that undergo molecular profiling but that are not enrolled into any of the investigational treatment arms will be enrolled into the NOS arm, which is considered to be a natural history arm. These patients do not have to meet any particular eligibility criteria. Individuals who meet the eligibility criteria for *EGFR* germline mutation testing (Section 3.4) but who do not have advanced cancer as defined in Section 3.1.1 are not eligible for the NOS arm.

This will allow data collection on these patients, linking their clinical information with their molecular profiling analyses. Frequency determination of each mutation, its association with clinical features, response to other standard and experimental treatments and overall outcome data will be collected. As future therapeutic protocols or treatment arms specific for their molecular profiles are developed at NIH or elsewhere, patients may be notified of their eligibility for these studies.

The NOS arm will consist of the following mixture of patients:

- Patients that do not meet the eligibility criteria for enrollment in the available treatment arms of this protocol.
- Patients that meet eligibility criteria for a particular arm but cannot be enrolled on it because of other reasons such as patient preference or drug availability issues, among others.

The NOS arm is considered a natural history arm in which the patients are allowed to receive a standard of care or experimental therapy of their choice, including but not limited to the following modalities:

- Patients will be allowed to participate on any available treatment clinical trial at NIH or elsewhere.
- Patients will be allowed to receive standard of care treatment at NIH under protocol 04-C-0165 (“Care of the Adult Oncology Patient, Center for Cancer Research, NCI;” Principal Investigator: [name].) or elsewhere.
- Patients will be allowed to receive best supportive care at NIH or elsewhere.

[figure not shown]
Patients on this arm will be followed either with clinic visits, phone interviews, or medical records review every 4 months (+/- 2 months). The patients will continue to be followed in this arm indefinitely, until death or until the patient decides to withdraw from the protocol.

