## **15.2 Sample Size/Accrual Rate**

With a maximum of 20 patients per stratum, up to 300 evaluable patients may be treated in specific arms. All patients in the ‘other’ (NOS) stratum will be evaluated and have their data analyzed by disease and type of treatment to the extent possible. As they are considered entirely exploratory, no specific targets for accrual will be used for the patients in the ‘other’ (NOS) stratum. For the secondary objective of determining the frequency of *EGFR* germline mutations in families with high susceptibility to lung cancer, we plan to enroll 15 families over a period of a year; however, specific accrual targets are not provided due to the exploratory nature of this endpoint.

In order to enroll up to 300 patients in the specific arms on the basis of molecular profiling results, it is anticipated that based on the rates of mutations that occur in the genes used for treatment assignments, approximately 600 patients may need to be enrolled onto the trial. It is anticipated that up to 10 patients per month may be enrolled onto this trial from all participating sites and in all diseases combined, and thus approximately five years may be required to enroll up to 600 patients. Far fewer patients may be enrolled if the treatments fail to allow accrual to the second stage of the trial or if some arms close to accrual due to feasibility issues.

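### The feasibility rate in section 15.1 counts successful profiles only, so it cannot show whether patients with an actionable profile started matched therapy, which primary objective 1.1.1 also covers

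*Combined protocol and SAP*

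**What the plan says.** Section 1.1 gives the first primary objective as "To determine the feasibility of the use of tumor's molecular profiling and targeted therapies in the treatment of advanced stage" NSCLC, SCLC and thymic malignancies. Section 15.1 restates the two primary objectives together as "to determine the feasibility and efficacy of the use of molecular profile directed therapies in the treatment of advanced thoracic malignancies", and then defines the measure: "The feasibility rate for the trial will be evaluated by determining the percentage of enrolled patients with a successful molecular profile determined". It gives no target, no definition of failure and no confidence interval for this rate.

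Other sections bear on it:

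- Section 5.5 places every profiled patient who does not enter a treatment arm in the NOS arm. That includes patients who satisfy an arm's criteria but "cannot be enrolled on it because of other reasons such as patient preference or drug availability issues".
- Section 5.3 says that "treatment decisions will be made in approximately 2 weeks from the time that the tumor samples were obtained". Timing does not enter the rate.
- Section 3.1.3 admits patients who already hold a successful profile. Section 3.1.2 admits people for germline testing only, and under section 5.1 they have no tumour biopsy for profiling.
- Section 15.1 also contains a rule, justified by feasibility, that closes an arm holding no more than one patient 18 months after the first enrolment.
- Section 15.2 gives the planned numbers: "With a maximum of 20 patients per stratum, up to 300 evaluable patients may be treated in specific arms", for which "approximately 600 patients may need to be enrolled onto the trial". On pace it adds: "It is anticipated that up to 10 patients per month may be enrolled onto this trial".

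**The concern.** The objective has two steps, obtaining a usable profile and using it to treat. The rate covers only the first. A patient with a matching alteration who meets an arm's criteria and still receives no matched drug is scored the same as one who is treated. So is a patient whose result arrives too late to use. A patient who enters with a profile in hand cannot fail the measure at all.

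What is at stake is how the first primary objective gets answered. A favourable rate could be reported as feasibility of the whole strategy although it carries no information on whether matched treatment could be delivered to those who qualified for it.

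**Working it through.** **1. The plan's own figures (sections 15.1 and 15.2).**

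- Treated ceiling: 15 strata × 20 = 300. With the EGFR-mutant NSCLC arm at its own maximum of 28: 14 × 20 + 28 = 308.
- Accrual: 600 / 10 per month = 60 months, the five years stated.
- Ceiling as a share of enrolment: 300/600 = 50.0%; 308/600 = 51.3%.

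**2. What the rate responds to.** Let N be patients enrolled, P those profiled successfully, A those with an actionable profile, and T those who start the matched arm. Section 15.1 defines P/N. Delivery of matched therapy is T/A. Since T does not appear in P/N, moving T from A (everyone treated) to 0 (nobody treated) leaves the feasibility rate unchanged.

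**3. Whether the planned ceiling sizes the problem.** The overall treated share is T/N = (P/N) × (A/P) × (T/A). The documents give no value for P/N or T/A and no overall A/P, so the rows below use assumed values.

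| P/N | A/P | T/A | T/N |
|---|---|---|---|
| 1.00 | 0.50 | 1.00 | 0.50 |
| 1.00 | 0.50 | 0.60 | 0.30 |
| 1.00 | 0.30 | 1.00 | 0.30 |

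The first row reaches the planned 50% with no failure of delivery. The second and third share the same section 15.1 rate (100%) and the same treated share (30%). In one, four in ten actionable patients go untreated; in the other, none do. Neither P/N nor T/N identifies T/A, so it has to be reported directly. Section 15.2 derives the 600 from mutation rates, which sit in A/P.

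**4. Early stopping.** If all 14 arms with a first stage of 9 and the one with a first stage of 10 stopped there, 14 × 9 + 10 = 136 would be treated. That is 136/600 = 22.7% if enrolment were held at 600. Section 15.2 expects far fewer to enrol in that case, and the shortfall would come from the stopping rule, not from failed delivery.

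**5. Crossover.** Section 5.4 counts a crossover patient as new in the second arm. With 30 or 60 such registrations (assumed), 300 arm places are 270 or 240 people, or 45% or 40% of 600. Arm totals are therefore not counts of persons treated.

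**6. Whether another element supplies T/A.**

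- The 18-month rule works at arm level, with a threshold of one patient. It closes accrual and does not enter the rate.
- The response analysis in section 15.5.2 leaves out patients who received no study drug, so it begins after delivery has succeeded.
- Section 15.4 gives mutation frequencies with exact intervals. These inform A/P and do not involve T.
- Section 4.1.1 records arm letters A to F at registration, including NOS. The raw material for T/A exists, but no such rate is specified.

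**The case against.** Section 15.1 can be read as a deliberate split, with profiling under feasibility and response to the assigned drug under efficacy. The earlier profiling study cited in section 2.1.1 lends support. There 66 of 86 patients (76.7%) received profile-based treatment, yet the feasibility conclusion drawn is about measuring targets. This explains the definition but does not close the gap. The objective and its restatement both name therapy, response is analysed only in those treated, and the 18-month rule shows that the protocol itself treats filling the arms as a feasibility matter.

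Several further points stand and limit both the concern and the remedy:

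- A patient with no matching alteration who goes to NOS is the schema working as designed.
- The arms stopped recruiting on 3/22/16 while profiling continued (sections 5.3 and 16.4), so later enrollees could not start an arm. From Amendment I the participating site, OHSU, stopped new NOS enrolment but kept enrolling to treatment arms (Précis, Design). A matched-start rate over everyone enrolled would be pushed down by the first and up by the second.
- Reasons for not starting and dates of treatment decisions are not among the follow-up items in section 5.11 or on the worksheet in Appendix J.
- Redefining a primary endpoint after treatment accrual has ended, with no threshold set in advance, would be improper. Added measures must be descriptive.

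**Conclusion.** The mismatch is real and worth correcting. The stated rate measures profiling feasibility and cannot show failure to deliver matched therapy to patients who qualified for it. This follows from the definitions and needs no numerical assumption.

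Its size cannot be derived. A reader might infer that the trial could report almost complete feasibility while most patients go untreated, or might take the distance between a high profiling rate and the 50% ceiling as the unmeasured part of the objective. The documents support neither inference. They state no profiling success rate. Failed biopsies would lower the rate, and so would germline-only enrollees if counted in the denominator, which section 15.1 leaves open. The plan allows up to half to be treated, and a lower share requires assumptions about stopping, enrolment or crossover. The ceiling mainly reflects mutation rates and stratum caps. Untreated patients who had an actionable profile and an open arm are an unknown part of the remainder.

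**What to change.** In section 15.1, keep the present rate, call it profiling feasibility, and add the following, by disease and with exact 95% confidence intervals:

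1. **Matched-start rate.** Among unique advanced-cancer patients with an actionable profile (meeting a molecular criterion in section 3.3) whose matched arm was open to accrual at the time, the proportion who started that arm.
2. **Patient flow, descriptive.** Enrolled, profiled, actionable, started. Count each person once despite crossover. Exclude germline-only enrollees and patients enrolled after the arms closed. Show OHSU separately from Amendment I onward.

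Take each arm's closing date from accrual records, because a note in section 4.1.1 under a 04/08/14 version date also describes the arms as closed. Report reasons for not starting, and the share of treatment decisions made within about two weeks of sampling, only where existing records hold them. State that any conclusion on objective 1.1.1 draws on both the profiling rate and the matched-start rate, and that the added measures are descriptive.

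The cost is a few lines of text and some record review for arm status and start dates. Arm assignments are already recorded at registration. The downside is a less favourable feasibility figure. No treatment rule changes.

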#### **13.1.1 Definitions**

Evaluable for toxicity. All patients will be evaluable for toxicity from the time of their first treatment.

Evaluable for objective response. Only those patients who have measurable disease present at baseline, have received at least one cycle of therapy, and have had their disease re-evaluated will be considered evaluable for response. These patients will have their response classified according to the definitions stated below. (Note: Patients who exhibit objective disease progression prior to the end of cycle 1 will also be considered evaluable.)

Evaluable Non-Target Disease Response. Patients who have lesions present at baseline that are evaluable but do not meet the definitions of measurable disease, have received at least one cycle of therapy, and have had their disease re-evaluated will be considered evaluable for non-target disease. The response assessment is based on the presence, absence, or unequivocal progression of the lesions.

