### **15.5.2 Evaluation of response**

All patients included in one of the experimental arms of the study must be assessed for response to treatment, even if there are major protocol treatment deviations. Each patient will be assigned one of the following categories: 1) complete response, 2) partial response, 3) stable disease, 4) progressive disease, 5) early death from malignant disease, 6) early death from toxicity, 7) early death because of other cause, or 9) unknown (not assessable, insufficient data). [Note: By arbitrary convention, category 9 usually designates the “unknown” status of any type of data in a clinical database.]

All of the patients who met the eligibility criteria for a particular treatment arm (with the exception of those who received no study medication) should be included in the main analysis of the response rate. Patients in response categories 5-9 should be considered to have a treatment failure (disease progression). Thus, an incorrect treatment schedule or drug administration does not result in exclusion from the analysis of the response rate. Precise definitions for categories 5-9 will be protocol specific.

All conclusions should be based on all eligible patients. Subanalyses may then be performed on the basis of a subset of patients, excluding those for whom major protocol deviations have been identified (e.g., early death due to other reasons, early discontinuation of treatment, major protocol deviations, etc.). However, these subanalyses may not serve as the basis for drawing conclusions concerning treatment efficacy, and the reasons for excluding patients from the analysis should be clearly reported. The 95% confidence intervals should also be provided.

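### Does the two-stage response rule lack a denominator because 15.1, 15.2 and 15.5.2 name different patient sets?

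*Combined protocol and SAP*

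**What the plan says.** **Stage 1 (15.1).** In 14 of the 15 arms, "the study will initially enroll 9 evaluable patients in each stratum and if 0 or 1 of the 9 have a clinical response", no more patients are accrued. The NSCLC/EGFR arm uses 10 evaluable patients and stops at 0 to 3 responses.

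**Who is evaluable (13.1.1).** Patients with measurable disease at baseline who "have received at least one cycle of therapy, and have had their disease re-evaluated will be considered evaluable for response". A note widens this: "Patients who exhibit objective disease progression prior to the end of cycle 1 will also be considered evaluable".

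**Total and final cut-off (15.1).** After a positive first look, "accrual would continue until a total of 20 patients have enrolled in that stratum" (28 in the EGFR arm). For the 14 arms, "if there were 5 or more responses in 20 patients, then this would be sufficiently interesting to warrant further study in later trials". No analysis set is named in that sentence.

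**Sample size (15.2).** After capping each stratum at 20, the section says "up to 300 evaluable patients may be treated in specific arms". Its next paragraph gives the same 300 as an enrolment target, without the word evaluable.

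**Analysis set (15.5.2).** The main response analysis takes all eligible patients except those who received no study drug. Early deaths and unknown responses (categories 5 to 9) count as failures. "All conclusions should be based on all eligible patients", and subset analyses may not support efficacy conclusions.

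**The concern.** A treated patient who dies or stops without re-evaluation or documented progression is outside the stage 1 count but is a failure in the 15.5.2 denominator. That can reverse a decision. Suppose the first 9 treated include 1 responder and 1 patient never re-evaluated, and the 10th treated patient responds. Counted on treated patients the first look is 1/9 (stop); counted on evaluable patients it is 2/9 (continue).

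At the final look, the word evaluable in 15.2 could be taken to mean recruiting until 20 evaluable patients are reached. The 15.5.2 set would then exceed 20, and the plan has no cut-off for a larger number.

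Response rate is a primary objective, and this rule decides it arm by arm. If the denominator were really open, it could be picked after the responses are known.

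**Working it through.** **1. Reproduce the plan's figures.** Inputs from 15.1: p0 = 0.10, p1 = 0.40, stage 1 limit r1/n1 = 1/9, final limit r/n = 4/20 (success at 5 or more). EGFR arm: p0 = 0.30, p1 = 0.60, 3/10, n = 28. The EGFR final cut-off is not stated. I use 13 or more of 28, because 12 gives alpha 0.0813 and 14 gives power 0.869, so only 13 meets both stated error rates.

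Early stopping under the null is P(X ≤ r1), X ~ Bin(n1, p0):
- 14 arms: 0.9^9 + 9 × 0.1 × 0.9^8 = 0.3874 + 0.3874 = 0.775 (plan: 77%).
- EGFR arm: 0.650 (plan: 65%).

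Success probability = Σ over k > r1 of b(k; n1, p) × P(Bin(n − n1, p) ≥ r + 1 − k). For the 14 arms at p = 0.10:
- k = 2: 0.1722 × 0.0896 = 0.0154
- k = 3: 0.0446 × 0.3026 = 0.0135
- k = 4: 0.0074 × 0.6862 = 0.0051
- k ≥ 5: 0.0009

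The sum is 0.0349, and the same formula at 0.40 gives power 0.9018. EGFR arm: alpha 0.0419, power 0.9122. The designs are sound with a single denominator.

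**2. Apply each section to its own subject.** Stage 1 is counted in the first n1 evaluable patients. Enrolment ends at 20 (28). The final count is over all treated, with unevaluable patients as failures.

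Let d be the unevaluable fraction and e the response rate among evaluable patients. The number u of unevaluable patients treated before the n1-th evaluable one is negative binomial (n1, 1 − d). Then

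P(success) = Σ_u NB(u) Σ_{k > r1} b(k; n1, e) × P(Bin(n − n1 − u, e(1 − d)) ≥ r + 1 − k).

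The plan does not say which population p0 and p1 describe, so both are shown: A, the rate among evaluable patients (e = p); B, the rate among all treated (e = p/(1 − d)). The values of d are assumptions.

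| Arm | d | alpha A | alpha B | power A | power B |
|---|---|---|---|---|---|
| 14 arms | 5% | 0.0298 | 0.0361 | 0.8867 | 0.9144 |
| 14 arms | 10% | 0.0250 | 0.0373 | 0.8653 | 0.9250 |
| 14 arms | 20% | 0.0166 | 0.0394 | 0.7977 | 0.9401 |
| EGFR | 5% | 0.0292 | 0.0435 | 0.8764 | 0.9277 |
| EGFR | 10% | 0.0195 | 0.0448 | 0.8185 | 0.9385 |
| EGFR | 20% | 0.0075 | 0.0470 | 0.6297 | 0.9485 |

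Alpha stays below 0.05 in every row. Power is lost only under A.

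**3. How often the stage 1 set would matter.** The chance under the null that the first n1 treated read stop while the first n1 evaluable read continue, at d = 5, 10 and 20% (A to B):
- 14 arms: 1.7 to 1.8%, 3.4 to 3.9%, 6.7 to 8.8%.
- EGFR arm: 4.0 to 4.3%, 7.8 to 9.0%, 14.9 to 20.3%.

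This compares the written rule with one the plan does not contain: 15.1 states its stop in evaluable patients.

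**4. The 300 in 15.2.** It is 15 × 20 = 300. Allowing for the EGFR arm's 28 it would be 14 × 20 + 28 = 308. So it is a rounded resource estimate, not a counting rule. Using it to recruit past 20 would contradict both the 20-enrolled stop in 15.1 and the 20-per-stratum cap in 15.2 itself.

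**The case for a change.** The strongest case for a change is that the coherent reading is nowhere written down and that the wrong choice is not harmless. If evaluable patients were used at both looks and p0 is the rate among all treated, alpha is 0.051 at 10% and 0.078 at 20% unevaluable in the 14 arms, and 0.090 and 0.188 in the EGFR arm. Such patients are plausible: restaging is every 6, 8 or 12 weeks, ECOG 2 is allowed, and 15.5.2 provides codes for early death and unknown response.

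The arithmetic stands, and so does the point that 15.1 lacks a pointer to 15.5.2. But the inflated alpha needs an evaluable-only final count, and 15.5.2 rules that out: a finding of 5 or more in 20 is an efficacy conclusion, and those must rest on all eligible treated patients. The final denominator is therefore not free to be chosen after the data.

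The power loss under reading A also stands, and it is sizeable in the EGFR arm at 20%. It depends on taking 40% and 60% as rates among evaluable patients, whereas 15.5.2 defines the trial's main response rate over all eligible treated patients. The affected group may also be small: 13.1.1 keeps early objective progressors in the evaluable set, and 13.1.4.3 asks that progression be documented even after treatment stops.

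**Conclusion.** The inconsistent labels are real, but they do not leave the rule undefined. Stage 1 is stated in evaluable patients, which 13.1.1 defines; the accrual ceiling is stated in enrolled patients; the set for conclusions is fixed by 15.5.2. Followed in that way, alpha is 0.017 to 0.039 in the 14 arms and 0.007 to 0.047 in the EGFR arm at 5 to 20% unevaluable. Power is at or above the design value if p1 is the all-treated rate. If p1 is the evaluable rate, it falls to 0.798 in the 14 arms and 0.630 in the EGFR arm at 20%. These figures rest on assumed unevaluable rates, on counting unevaluable patients as non-responders, and, for the EGFR arm, on a 13-of-28 cut-off the plan does not state.

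Recruitment to the treatment arms ended on 3/22/16, so new wording could not alter a stage 1 decision, and the set for conclusions is already fixed. A careful analyst will in any case report, for each arm, which patients were counted at stage 1 and the responders over both sets. The word evaluable beside the 300 in 15.2 is a slip. No change to the plan follows.
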